13.13.10. Overview of data collection

Target Population	Measure	Data collection	Items / Time Required	PERMIT Study Step	Frequency	PICU Discharge or 30 days		
						Pre-PICU Baseline	During PICU	PICU Discharge or 30 days
PERMIT champions	Weekly debrief discussion	Central PERMIT Research Team	30 mins	1,2,3	Weekly	n/a		
PICU health care professionals	Online survey	Central PERMIT Research Team	15 mins	1,2,3	3 times per participant	n/a		
	Interviews	Central PERMIT Research Team	≤60 mins	3	Once per participant	n/a		
CYP (clinical data from PICANet)	Various	Local PERMIT Research Team (downloaded from PICANet)	Various	2	Various		X	
CYP (clinical data in addition to PICANet)	Height and Weight Z score (admission and discharge)	Local PERMIT Research Team		2	Twice per participant		X	
	Pain Visual Analogue Scale (admission and discharge)	(collected from medical records using case report form)	1 item / 1 minute	2	Twice per participant		X	
	PELOD-2 score	Local PERMIT Research Team (collected with validated tools)	2 minutes	2	Daily		X	
	Children's Chelsea Critical Care Physical Assessment Tool (cCPAx)		5 minutes	2	Daily	X	X	X
	BRADEN-QD		7 items / 5 minutes	2	Daily		X	
	Cornell Assessment of Pediatric Delirium (CAP-D)		8 items / 4 minutes	2	Daily		X	
	COMFORT Behavioral Score		8 items / 3 minutes	2	Daily		X	
Pediatric Overall Performance Category (POPC) and Pediatric Cerebral Performance Category (PCPC)	2 items / 6 minutes		2	Twice per participant	X ¹	X		
PERMIT intervention	Patient acuity level		Local PERMIT		2	Daily		X
Prescribed ERM activity level and specific ERM activities		2		Daily		X		
Delivered ERM activity levels and specific ERM activities (including timing, duration, number and type of staff or family member assisting)		2		Daily		X		

17/21/06: The PERMIT Feasibility Study

Target Population	Measure	Data collection	Items / Time Required	PERMIT Study Step	Frequency	Pre-PICU Baseline	During PICU	PICU Discharge or 30 days
data	Reasons for deviating from the prescription, where relevant	Research Team (collected with screening log and case report form)		2	Daily		X	
	Use of pause and reassess criteria			2	Daily		X	
	Safety and adverse events			2	Daily		X	
	Any intervention / manual tailoring proposed or undertaken within the site			2	Daily		X	
CYP (outcome measurement tools)	Pediatric Quality of Life Inventory (PedsQL) TM Infant Scales Version 4.0 – Acute (Aged: 1-23 months) OR PedsQL TM Generic Core Scales Version 4.0 - Acute (Aged: 2 years+)	Local PERMIT Research Team collect the data from parents/legal guardians	36 items / <7min 45 items / <10 min 21/23 items / <5 min	3	Twice per participant	X ¹		X
	PedsQL TM Multi-dimensional Fatigue Scale Version 3.0 - Acute		18 items/ 5 min	3	Twice per participant	X ¹		X
	PedsQL TM Pediatric Pain Questionnaire (PPQ) TM		1 item / <1 min	3	Once per participant			X
Parent/legal guardian (interview)	Interview	Central PERMIT Research Team	≤60 mins	3	Once per participant			X
Parent/legal guardian (outcome measurement tools)	Parent Stressor	Local PERMIT Research Team (collected with validated tools)	30 items / 10 mins	3	Once per participant		X	
	Scale: PICU							
	EMPATHIC-30		30 items / <15 mins	3	Once per participant		X	
	PedsQL TM Family Impact Module Version 2.0		36 items / 5 min	3	Twice per participant	X ¹		X
	Patient Health Questionnaire-4 (PHQ-4)		4 items / 2 min	3	Once per participant			X

[figure not shown]
¹ Baseline pre-PICU score will be calculated retrospectively.

13.14. Data management, transfer and storage

This section describes the data management, transfer and storage of the following data:

- All consent and assent forms
- Weekly debrief with PERMIT champions (signed consent forms and researcher notes).
- Surveys of PICU health care professionals (survey responses and names / email addresses of those willing to take part in an interview).
- Interviews with PICU health care professionals (signed consent forms, audio recordings, transcripts).
- CYP clinical data – collected routinely through PICANet (electronic downloaded data).
- CYP clinical data – collected in addition to PICANet (validated data collection tools and case report forms).
- PERMIT intervention data (screening logs and case report forms).
- CYP and parent outcome measurement tools (validated outcome measurement tools).
- Interviews with parents/legal guardians (audio recordings, transcripts).

13.14.1. **Figure 3 - Data Management**

13.14.2. Consent and assent forms

Signed consent forms for PERMIT champions, PICU health care professionals, parents/legal guardians, and CYP assent forms, will be held by the Local PERMIT Research Team and the forms will be stored in the PERMIT study file at each site, which in turn is stored in a secure research office. A password protected database at the site will maintain a record of consenting PERMIT champions.

Electronic scanned copies of the completed consent forms will be shared via nhs.net email with the Central PERMIT Research Team who will be conducting the interviews. These will be stored electronically in a central PERMIT database.

13.14.3. Weekly debrief with PERMIT champions

The paper-based notes from the weekly debrief will be scanned and stored electronically in a password protected folder on the Central PERMIT Research Team database. The researcher will also type up the notes and save them in the same location and share a copy of the notes with the Local PERMIT Research Team. The typed up notes may be uploaded into a password protected NVivo file (v11 or v12; software for qualitative/mixed-methods research) to allow co-ordination of analysis. The original paper-based notes will be destroyed after the typed up notes have been checked against them. All electronic files will be retained in a secure archive setting for 10 years to facilitate future analysis and publication of the study material.

13.14.4. Surveys of PICU health care professionals:

The three brief online surveys will be accessible via an individual secure web-based link (SMARTSurvey platform). Only members of the Central PERMIT Research Team will have access to the survey data. Data within SMARTSurvey will be downloaded and saved on password protected files for analysis. Survey data within SMARTSurvey will be deleted after data download. All other records (e.g. downloaded files) will be retained in a secure archive setting for 10 years to facilitate future analysis and publication of the study material. Respondents will only provide personal identifying data if they are happy to be contacted about participation in an interview. This data will be separated by the Central PERMIT Research Team and stored separately on an electronic password protected database and will not be included in the data analysis.

13.14.5. PICU health care professional interviews

Researchers from the Central PERMIT Research Team conducting the interviews with PICU health care professionals may be based at Universities of Newcastle, Northumbria, Birmingham or at Birmingham Women and Children's NHS Foundation trust.

Some health care professionals will express interest in taking part in an interview by providing their name and email address via the brief online surveys. The log of volunteers from survey responses will be created and maintained by the Central PERMIT Research Team, taking this information from completed surveys. The information will not be able to be linked to health care professionals' survey responses. It will be added to a separate password protected electronic folder for access only by the researcher from the Central PERMIT Research Team conducting the interviews with health care professionals.

Some health care professionals will respond to an email invitation to take part in an interview which will be sent by the Local PERMIT Research Team. The participant information sheet instructs individuals who want to take part to contact the Central PERMIT Research Team directly via email with their completed consent forms. Therefore, there is no transmission of health care professional details between the Central and Local PERMIT Research Teams.

The audio recordings of the interviews will be removed from the recording device at the earliest opportunity and stored on a secure password protected secure folder on a University or NHS firewall protected secure computer server, using a unique participant ID number. Audio files will be destroyed at the end of the PERMIT study.

Audio recordings will be transferred electronically to a professional transcription service provider, with whom a confidentiality agreement will already be signed and in place as part of providers' ongoing contracts with the relevant universities. Files transferred to the transcription service will be password protected and the password will be emailed separately to the file. The transcription company will return an anonymised transcription via a password protected file to the Central PERMIT Research Team. Once the transcriptions have been checked against the recordings for accuracy, any remaining identifying information will be removed and replaced with code words (e.g. for key locations). Transcripts will be retained in a secure archive setting for 10 years to facilitate future analysis and publication of the study material. Transcribed word documents will be identified by the unique participant ID. Documents can then be uploaded to NVivo v11 or v12 for analysis. These will be shared as per the analysis plan with other members of the Central PERMIT Research Team to allow co-ordination of analysis.

We do not plan to return transcripts to participants for comment or correction. The interviewer will double check understanding within the interview process to help ensure that the correct interpretation has been made. Transcripts and field notes will be fully anonymised before data analysis begins. All electronic data will be accessible only by the Central PERMIT Research Team.

13.14.6. CYP clinical data – collected routinely through PICANet (electronic downloaded data):

The CYP participants will have a unique PERMIT study ID [local site code + sequential patient number;], local patient IDs [NHS number and own hospital patient identification number] and PICANet study ID [provided by PICANet].

Local sites will be able to access the required PICANet data via a customised download from the PICANet database using the PERMIT study ID. No identifiable patient data will be included in this customised download (date of birth will be converted into age in days). The PICANet data download will be uploaded by Local PERMIT Research Team to the REDCAP database to combine with the PERMIT study case report form (CRF) data.

13.14.7. CYP clinical data – collected in addition to PICANet (validated data collection tools and CRFs):

Local sites will complete the validated data collection tools and CRFs listed in section 9.6.5 and the CYP clinical data section of the table at 9.6.11 (details in appendix 1) for all enrolled patients using the PERMIT study ID on each record.

Dependent on local site preference, the validated data collection tools and CRFs will be accessible both:

- Via direct electronic data entry (via web-accessed iPad or computer) to input directly into the secure REDCAP database using the PERMIT study ID for patient identification only; and/or
- Via paper-based format. Paper data collection tools and CRFs will be collated and stored in patient-specific site files. Local sites will be responsible for the safe and secure storage of these primary documents (locked in a filing cabinet or office within the PICUs or research offices). If not using iPads/computer direct entry, local sites will input paper-based data onto the REDCAP computer database using the PERMIT study ID for patient identification only. No identifiable patient data will be uploaded to REDCAP or shared with the PERMIT Trials Office at the University of Birmingham.

The Central PERMIT Research Team will access the de-identified data in the REDCAP database.

Data contained within REDCAP will be transferred securely to the University of Birmingham computer server within the PERMIT study database for statistical analysis in the PERMIT Trials Office at the University of Birmingham.

13.14.8. PERMIT intervention data (screening logs and CRFs):

The Local PERMIT Research Team will create an electronic screening log at each site to record all screening for eligibility for the PERMIT study. The log will include local patient IDs [NHS number and own hospital patient identification number]. This record will remain at the local site only and will not be shared with the Central PERMIT Research Team. For patients that fulfil **all** inclusion criteria and **no** exclusion criteria **and** consent is obtained from parents/legal guardians, local research staff will add the patient to the enrolment log.

PERMIT intervention data will be transferred from the CRFs and entered at the local site into the REDCAP database using the patient identification number with no identifiable information. Data contained within REDCAP will be transferred securely to the University of Birmingham computer server within the PERMIT study database for statistical analysis in the PERMIT Trials Office at the University of Birmingham.

13.14.9. CYP and parent/legal guardian outcome measurement tools (validated outcome measurement tools):

The data from the outcomes measurement tools will be entered into REDCAP at the local site using the patient identification number with no identifiable information.

Following data entry into REDCAP, any paper based records of outcome assessment tools will be stored securely in the Local PERMIT Research Team office to allow for any data queries to be addressed, to be disposed of securely at the end of the PERMIT study by the Local PERMIT Research Team.

The Central PERMIT Research Team will access the de-identified data in the REDCAP database.

Data contained within REDCAP will be transferred securely to the University of Birmingham computer server within the PERMIT study database for statistical analysis in the PERMIT Trials Office at the University of Birmingham.

13.14.10. Interviews with parents/legal guardians (audio recordings, transcripts):

The Local PERMIT Research Team will create a local participant log of parents/legal guardians who consent to an interview. Local storage of the participant log will be the responsibility of the Local PERMIT Research Team. These will be kept in electronic, password protected files within NHS secure servers, or locked filing cabinet within a secure office facility.

Researchers from the Central PERMIT Research Team conducting the interviews with parents/ legal guardians may be based at the University of Birmingham or at Birmingham Women and Children's NHS Foundation trust.

The Local PERMIT Research Team will transfer the log information via nhs.net encrypted email attachment to the Central PERMIT Research Team. This will include the parent/legal guardian name,

the child's name¹, contact information (name, telephone number). This information will be stored in a password protected electronic file. No patient identifiable information will be shared outside the Central PERMIT Research Team.

The audio recordings of the interviews will be removed from the recording device and stored on a secure password protected secure folder on a University or NHS firewall protected secure computer server, using a unique participant ID number. Audio files will be destroyed at the end of the PERMIT study.

Audio recordings of the interviews will be transferred electronically to a professional transcription service provider, with whom a confidentiality agreement will already be signed and in place as part of providers' ongoing contracts with the relevant universities. Files transferred to the transcription service will be password protected and the password will be emailed separately to the file. The transcription company will return an anonymised transcription via a password protected file to the Central PERMIT Research Team. Once the transcriptions have been checked against the recordings for accuracy, any remaining identifying information will be removed and replaced with code words (e.g. for key locations). Transcripts will be retained in a secure archive setting for 10 years to facilitate future analysis and publication of the study material. Transcribed word documents will be identified by the unique participant ID. Documents can then be uploaded to NVivo v11 or v12 for analysis. These will be shared as per the analysis plan with other members of the Central PERMIT Research Team to allow co-ordination of analysis.

We do not plan to return transcripts to participants for comment or correction. The interviewer will double check understanding within the interview process to help ensure that the correct interpretation has been made. Transcripts and field notes will be fully anonymised before data analysis begins. All electronic data will be accessible only by the Central PERMIT Research Team.

13.15. Confidentiality and data protection

The only identifiable participant information that will be shared by the Local PERMIT Research Team to the Central PERMIT Research Team will be the names, contact details and consent forms of the parents/legal guardians who have agreed to take part in interviews and the names of their children.

No other identifiable patient data will be transferred to the Central PERMIT Research Team or PERMIT Trials Office for the PERMIT feasibility study. De-identified pseudonymised data will be stored securely in a REDCAP database or nested within the PICANet database. Currently, all patients admitted to PICU have data recorded via the Paediatric Intensive Care Audit Network (PICANet). PICANet has permission to collect identifiable patient data under section 251 of the NHS Act 2006 (originally enacted under Section 60 of the Health and Social Care Act 2001). We will use the PICANet data to supplement and reduce the burden of data collection for PERMIT.

As PICANet is part of the Health Quality Improvement Partnership (HQIP), therefore we intend to make a release of data request, and a customised data collection request to HQIP in order to gain access to unidentifiable routine PICANet data and collect the additional data required for this study.

¹ Public and patient involvement and engagement work informs us that parents/ legal guardians find it important that anyone addressing them is aware of their child's name as this feels more personal.

Personal data recorded on all documents will be regarded as strictly confidential and will be handled and stored following the General Data Protection Regulation and Data Protection Act 2018.

On the CRFs and for correspondence between the PERMIT Trials Office and the participating sites, participants will always be identified using only their unique study identification number.

The Local PERMIT Research Team must maintain documents not for submission to the PERMIT Trials Office (e.g. Participant Identification Logs) in strict confidence. In the case of specific issues and/or queries from the regulatory authorities, it will be necessary to have access to the complete study records, provided that participant confidentiality is protected.

The PERMIT Trials Office will maintain the confidentiality of all participants' data and will not disclose information by which participants may be identified to any third party. Representatives of the Central PERMIT Research Team, PERMIT Trials Office and sponsor may be required to have access to participant's notes for quality assurance purposes, but participants should be reassured that their confidentiality will be respected at all times.

The Chief Investigator ([name]) will act as the data custodian for the PERMIT feasibility study.

13.16. Archiving

At the end of the study, the Chief Investigator will archive all centrally-held study-related documents securely for a minimum of ten years in accordance with ICH-GCP guidelines.

It will be the responsibility of the Principal Investigators at each site to ensure all essential study documentation, and source documents (e.g. study files, copies of CRFs) at their sites are securely retained for at least 10 years.

All archived documents, held centrally and locally, should be available for inspection by appropriate authorities upon request.

13.17. ADVERSE EVENT REPORTING

13.17.1. Definitions

As the current study is not investigating medical products, adverse event (AE) reporting will follow the Health Research Authority guidelines on safety reporting in non-clinical trial investigational medicinal product studies.

13.17.2. Adverse event

Events and complications associated with the patient's underlying medical condition will not be considered AEs. An AE is defined as any untoward medical occurrence in a study participant.

As patients are critically ill, it is expected that unrelated AEs will occur as part of hospital stay. Therefore, AEs are only defined in relation to changes occurring before, during and after an ERM intervention period.

The PERMIT intervention manual contains a risk assessment procedure and 'pause and reassess' criteria to consider during ERM intervention. Local PERMIT Research Teams will record each time a pause and reassess criterion is triggered in the daily ERM CRF. An AE will be defined as an event outside of the pause and reassess safety rules definition.

13.17.3. A serious adverse event (SAE) is defined as an untoward occurrence that:

- Results in death;
- Is life-threatening;
- Requires hospitalisation or prolongation of existing hospitalisation*;
- Results in persistent or significant disability or incapacity;
- Consists of a congenital anomaly or birth defect; or
- Is otherwise considered medically significant by the investigator.

*Hospitalisation is defined as an inpatient admission regardless of length of stay, even if the hospitalisation is a precautionary measure for continued observation. Hospitalisations for a pre-existing condition, including elective procedures that have not worsened, do not constitute an SAE.

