13.12.2. Secondary outcomes

[figure not shown]
- **Acceptability of all data collection forms, outcome measurement tools and the PERMIT intervention as a whole:**
 - We will use the weekly debrief with PERMIT champions, interviews with PICU health care professionals and interviews with parents/legal guardians to assess acceptability of all data collection forms, outcome measurement tools and the PERMIT intervention as a whole. These data, along with the data from the data collection forms and outcome measurement tools themselves, will also provide us with an indication of the potential impact of the PERMIT intervention on CYP and parents/legal guardians.
 - **Number of ERM activities prescribed per CYP following patient acuity screening:**
 - The Local PERMIT Research Team will record the number of ERM activities prescribed to CYP follow daily acuity screening daily.
 - **Number of ERM activities delivered per CYP:**
 - The Local PERMIT Research Team will convert prescribed ERM activity to delivered ERM activity and will calculate this on a daily basis.
 - **Safety and adverse event rates during an ERM activity:**
-

17/21/06: The PERMIT Feasibility Study

- The Local PERMIT Research Team will undertake safety and adverse event reporting by day, by patient and by PICU.
- **Safety and adverse event rates throughout the whole PERMIT intervention study period:**
 - The Local PERMIT Research Team will undertake safety and adverse event reporting by day, by patient and by PICU.

17/21/06: The PERMIT Feasibility Study

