- **Screening, eligibility and recruitment data:** Daily screening of CYP on PICU by the Local PERMIT Research Team to calculate the number of patients fulfilling inclusion eligibility and number of patients approached, consented/declined for the study.

Once parents/ legal guardians (and CYP where appropriate) have consented patients will receive the PERMIT intervention until PICU discharge. The Local PERMIT Research Team will use the PERMIT Case Report Form for each individual CYP to collect the following data about the PERMIT intervention at ward rounds, ERM intervention sessions and through discussion with local clinicians:

- Patient acuity level
- Prescribed ERM activity level and specific ERM activities

-
- Delivered ERM activity levels and specific ERM activities (including timing, duration, number and type of staff or family member assisting)
 - Reasons for deviating from the prescription, where relevant
 - Use of pause and reassess criteria
 - Safety and adverse events
 - Any intervention / manual tailoring proposed or undertaken within the site

13.13.7. CYP outcome measurement tools:

The Local PERMIT Research Team will collect the following data from parents/legal guardians as the child's proxy using validated outcome measurement tools (see Appendix 1), previously used in the PICU population. The outcome measurement tools will be administered via the preferred communication methods of the parent/legal guardian e.g. face to face, telephone, videoconference, or paper-based or electronic. The information will be entered into the PERMIT study RedCAP database.

CYP outcomes will be measured at two time points:

During PICU admission. Parents/legal guardians will provide a retrospective report based on their child's pre-admission status (two weeks before) by completing: (1) Pediatric Quality of Life Inventory PedsQL™ Infant Scales Version 4.0 – Acute (Aged: 1-23 months) OR PedsQL™ Generic Core Scales Version 4.0 - Acute (Aged: 2 years+); and (2) PedsQL™ Multi-dimensional Fatigue Scale Version 3.0 - Acute

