13.17.5. Reporting and recording

AEs and SAEs will be recorded and reported for each patient until PICU discharge or 30 days after admission (whichever is earlier). All reported adverse events will be recorded in the medical notes of the patients.

Adverse events expected within the trial population during include the events listed below:

- Unplanned extubation
- Unplanned extubation requiring reintubation
- Unplanned removal of any other indwelling line, tube or drain (eg arterial line, central line, urinary catheter or chest drain).
- Unplanned removal of any other indwelling line, tube or drain requiring re-insertion
- Discomfort or Pain
- Ventilator Asynchrony
- Bradycardia requiring intervention
- Hypoxia/desaturation requiring intervention
- Fall

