13.21.3. Project oversight committee/trial steering committee

An independent trial oversight committee has been appointed by the NIHR in keeping with standard structure and definitions. The Trial Steering Committee will be responsible for overall supervision on behalf of the Sponsor and Funder, and will ensure that it is conducted in accordance with the rigorous standards set out in the Department of Health's Research Governance Framework for Health and Social Care and the Guidelines for Good Clinical Practice. The Trial Steering Committee will comprise the Chief Investigator plus independent members (including independent patient and public involvement (PPI) representatives). TSC meetings will take place at the start and after the feasibility study, and at any other time determined by the independent Chair.

Title	First name	Last name	Job Title	Expertise
[name]	Consultant in PICU	Chair, Clinician, Trialist
[name]	Professor of Paediatric Intensive Care	Clinician, Trialist
[name]	Senior Lecturer Health Services Research	Qualitative Researcher
[name]	Parent representative	PPI representative
[name]	Professor of Medical Statistics	Statistician

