13.21.4. Data monitoring and ethics committee (DMEC)

An independent DMEC has been appointed by the NIHR in keeping with standard structure and definitions. An independent DMEC will monitor recruitment and retention, adherence with the intervention and patient safety. Meetings will take place immediately prior to TSC meetings.

17/21/06: The PERMIT Feasibility Study

Title	First name	Last name	Job Title	Expertise
[name]	[name], Clinician, Trialist
[name]	Senior Statistician	Statistics
[name]	Paediatric Intensive Care consultant	Clinician

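### The Phase 3 adverse-event rules in section 13.17 do not match the safety outcomes in 13.12.2, and followed as written they may undercount adverse events

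*Protocol*

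**What the plan says.** All references are to the Phase 3 part of the protocol unless stated.

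- **AE definition (13.17.2).** The section opens by excluding events and complications linked to the underlying condition, then gives a general definition covering every untoward medical event in a participant. It next narrows this: "AEs are only defined in relation to changes occurring before, during and after an ERM intervention period". It ends with: "An AE will be defined as an event outside of the pause and reassess safety rules definition". The same section says that each pause-and-reassess trigger goes on the daily ERM case report form (CRF).
- **Expected AEs (13.17.5).** The list includes unplanned extubation, line or tube loss, pain, ventilator asynchrony, bradycardia requiring intervention, "Hypoxia/desaturation requiring intervention" and falls.
- **Safety outcomes (13.12.2).** There are two: one for rates during an ERM activity, and one titled "Safety and adverse event rates throughout the whole PERMIT intervention study period".
- **End of recording (13.17.5).** "AEs and SAEs will be recorded and reported for each patient until PICU discharge or 30 days after admission (whichever is earlier").
- **End of intervention (13.13.6).** After consent, "patients will receive the PERMIT intervention until PICU discharge". This section and the table in 13.13.10 list use of the pause criteria, and safety and adverse events, as two separate daily items.
- **Planned summary (13.20.3).** It covers the number and rates of AEs and the proportion of patients with one. Pause triggers are not mentioned.

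**The concern.** Monitoring safety is a stated objective (13.9.2, objective iv), and the study is meant to prepare a definitive randomised trial. The AE rate it reports will be read as evidence on harm. If the definition of an AE is narrower than the outcome it feeds, a low rate partly reflects the counting rule. Most of these are collection rules. An event outside the session window, or after the recording stop, may never be entered on an AE form, and a later analysis plan cannot recover it.

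**Working it through.** The plan states no AE rate, sample size or precision tied to safety, so there is no figure to reproduce. The check is mainly textual.

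**1. Session window against the whole-period outcome.** Outcome 1 counts events during an ERM activity. Outcome 2 is meant to count over the whole intervention period. Under 13.17.2 an AE exists only in relation to an ERM intervention period. That term is not defined. Reading it as a session is the natural reading but not the only one, and no length is given for the time before or after. On that reading:

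- outcome 2 = outcome 1 + events in an undefined before/after margin + any SAEs.

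SAEs belong in this sum because their definition in 13.17.3 carries neither the session window nor the pause exclusion. A non-serious event away from a session meets the general definition in 13.17.2 but fails the narrower one in the same section, so a site cannot follow both.

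**2. Underlying-condition exclusion against causality grading.** Section 13.17.4 sets five levels of relatedness. The middle level is for events where another cause is equally likely. Section 13.17.2 removes events associated with the underlying condition before that grading. In critically ill children, many events that belong in the middle level could be removed first.

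**3. Pause-and-reassess triggers.** They are recorded (13.17.2, 13.13.6, 13.13.10), placed outside the AE definition (13.17.2), and named in neither the outcomes (13.12.2) nor the planned summary (13.20.3). If a trigger is also an event listed in 13.17.5, then 13.17.2 takes out of the AE count what 13.17.5 lists as an expected AE. Whether any such overlap exists cannot be checked, because the intervention manual is not shown.

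**4. Day-30 stop against intervention to discharge.** For a child still in PICU after day 30, 13.17.5 ends AE and SAE recording while 13.13.6 continues both the intervention and the daily safety item.

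For scale only, section 8.12 (Phase 1b) says 40-45% of PICU patients stay at least 3 days and 20% stay more than 7. It gives no figure for 30 days. Take S(3) = 0.40 or 0.45 and S(7) = 0.20, and extrapolate the share of stays of at least 3 days that exceed 30 days, S(30)/S(3):

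- Exponential tail: (S(7)/S(3))^(27/4). This gives 0.5^6.75 = 0.9%, or 0.444^6.75 = 0.4%.
- Pareto tail: (30/3)^(-a), with a = ln(S(3)/S(7))/ln(7/3). This gives a = 0.818 and 15.2%, or a = 0.957 and 11.0%.
- Weibull and lognormal curves through the same two points fall between.

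| Assumed tail | Share beyond day 30 | Expected among 30 children |
|---|---|---|
| Exponential | 0.4-0.9% | 0.1-0.3 |
| Weibull | 1.0-3.6% | 0.3-1.1 |
| Lognormal | 4.3-8.0% | 1.3-2.4 |
| Pareto | 11.0-15.2% | 3.3-4.6 |

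The range of 0.1 to 4.6 children reflects the choice of tail. It also assumes that the recruited children resemble all PICU patients staying at least 3 days.

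**The case against.** The strongest reply is that the rules form a sensible two-tier scheme for critically ill children. Unrelated events are expected, a pause trigger is logged as such, and something beyond it is an AE. Several parts of this reply stand.

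- **Triggers are not lost.** A reader might infer that pause events disappear, or that mobilisation harms are screened out so that the AE rate falls to near zero. The documents do not support this. Triggers are on the CRF, the outcome titles refer to safety as well as AEs, and their tabulation could be left to the promised statistical analysis plan. Extubation, line loss and falls remain listed AEs. A near-zero rate would need full overlap with a manual that is not shown, and no other AEs.
- **The two outcomes can differ.** A reader might infer that they must coincide. The before/after margin and the SAE wording allow a difference.
- **Day 30 is not proof of missing data.** A reader might infer that long-stay children are treated with no safety recording. Sections 13.13.6 and 13.13.10 list daily safety data during the PICU stay, so this is a conflict between sections. Day 30 also fits the study's one-month follow-up, although that does not reconcile the text.
- **Oversight.** A reader might infer that no safety review can occur during delivery, since for the data monitoring and ethics committee (DMEC) "Meetings will take place immediately prior to TSC meetings". But "TSC meetings will take place at the start and after the feasibility study, and at any other time determined by the independent Chair". SAEs go to the chief investigator and sponsor within 24 hours (13.17.6), and urgent safety measures are provided for (13.17.7). A fixed extra review would be a preference, not the correction of an error.

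The reply does not remove the mismatch between 13.17.2 and the whole-period outcome, the unassigned triggers, or the conflict over the stop date.

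**Conclusion.** The concern holds as an inconsistency that should be fixed. Three mismatches are in the text: a session-tied AE definition against a whole-period outcome (and against the general AE definition in the same section); pause triggers that are recorded but assigned to no named outcome or summary; and a recording stop that can precede the end of the intervention. The first rests on reading an ERM intervention period as a session. The direction is towards undercounting AEs, chiefly in the whole-period outcome. The size cannot be stated. The documents give no AE or trigger rate, overlap between triggers and listed AEs is unknown, and the day-30 gap probably affects few of the 30 children. AE rates are secondary, descriptive outcomes here. The three primary outcomes (implementation, recruitment, completion of outcome tools) are unaffected.

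**What to change.** Leave the pause criteria and clinical care unchanged, and change only what is recorded and counted.

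1. Reconcile 13.17.2 with 13.12.2 and 13.17.5. Record the listed events and all SAEs from enrolment regardless of session timing. State the before/after window, flag whether each event fell inside it, and grade causality under 13.17.4 afterwards instead of excluding events beforehand. The flagged events then give the session-related rate, and all recorded events give the whole-period rate.
2. Name pause-and-reassess triggers as a safety outcome in 13.12.2 and in the summary in 13.20.3. Count as an AE any trigger that matches the list in 13.17.5, in place of the sentence that puts such events outside the definition.
3. Reconcile 13.17.5 with 13.13.6 and 13.13.10 so that AE and SAE recording lasts as long as the intervention is delivered.

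The cost is amendment wording, slightly more form completion at three sites, and a higher reported AE rate. The trigger data are already being collected. If enrolment has begun, the report should state which definition applied to which children.
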